9.2.2 Assessments and documentation of adverse events

The Sponsor-Investigator must collect all AEs for each subject from the time of the start of device procedure preparation up to 1 week following the end of subject study participation, whether or

not deemed related to the investigational device or procedure. All AE data will be recorded on the CRF.

All AEs will be followed until the event has subsided or, in case of permanent impairment, until the event stabilizes, and the overall clinical outcome has been ascertained.

The Sponsor-Investigator must document all device failures, malfunctions, and use errors, including the assessment whether the event is considered a near incident (ADE) using the CRF.

9.2.3 Reporting of serious adverse events and near incidents

The definition of SAE is provided in Section 9.1. These include device deficiencies that may have led to a SAE if a) suitable action had not been taken or b) intervention had not been made or c) if circumstances had been less fortunate. These are handled under the SAE reporting system.

- Notification of the IRB: Notification of the IRB about all relevant events (e.g., SAEs, near incidents, UADEs, device failures, device malfunctions) will be performed by the Sponsor-Investigator according to all applicable requirements.
- Notification of the authorities: The processing and reporting of all relevant events (e.g., SAEs, near incidents, UADEs, device failures, device malfunctions) to the authorities will be done by the Sponsor-Investigator according to all applicable regulations.

9.2.4 Expected adverse events

For this study, the applicable reference document is the most current version of the Risk analysis for the *VioTM* documented in Enspectra Health's quality system. The expectedness of AEs will be determined by the Sponsor-Investigator according to the applicable reference document and according to all local regulations. See the Section 1.4.2 for a list of expected adverse events.

9.3 Randomization codes and unblinding procedures

All enrolled subjects will undergo imaging with the *VioTM*. Subject group, therefore, will not be randomized nor blinded.

9.4 Stopping rules

Safety findings may trigger a temporary suspension of enrollment until an *ad hoc* safety review is conducted to determine whether the study should continue per protocol, proceed with caution, be further investigated, be discontinued, or be modified then proceed.

A safety review may be triggered by the occurrence of a UADE, or the occurrence or increased frequency of any situation the Sponsor-Investigator deems to be a trigger. Any findings shall be reported to the designated employees of Enspectra Health, who will then conduct a safety review and determine what steps will be taken.

The study may be discontinued at any time by the IRB, the FDA, or other government agencies as part of their duties to ensure that research participants are protected.

Participation of individual subjects may be terminated for multiple reasons, including failure to follow the Investigator's or designee's instructions, revelation of inaccurate information provided

during the screening process, safety reasons, subject is experiencing clear stress or pain (but the subject does not want to withdraw), or any scenario in which the Investigator judges it to be in the subject's best interest to terminate that subject's participation.

9.5 *Medical monitoring*

A medical monitor will be appointed for the study. The medical monitor will be a physician who is not involved in conducting the study and who has no or minimal conflict of interest. The medical monitor is responsible for ongoing monitoring of adverse event reports to identify safety concerns quickly. The medical monitor may also serve as a resource to the Sponsor-Investigator for advice about management of adverse events.

10 Data handling and record keeping

10.1 *Confidentiality*

All records identifying the subject will be kept confidential and, to the extent permitted by the applicable laws and/or regulations, will not be made publicly available.

Subject names will not be supplied to any people or organizations outside of Enspectra Health or authorized study staff. Within Enspectra Health, only the designated custodian(s) of the data shall have access to the subject names. Only the subject code will be recorded in the CRF. Study findings stored on a computer will be stored in accordance with local data protection laws. As part of the informed consent process, the subjects will be informed in writing that representatives of the Sponsor, IRB, or regulatory authorities may inspect their medical records to verify the information collected, and that all personal information made available for inspection will be handled in strictest confidence and in accordance with local data protection laws.

If the results of the study are published, the subjects' identities will remain confidential. The Sponsor-Investigator will maintain a list to enable subjects to be identified.

10.2 *Source documents*

Screening information, baseline information, recording of data, and information about subject completion of the study will be recorded directly on the CRF. As needed, information about device deficiency or malfunction, protocol deviations, or adverse events will also be recorded on the CRF. The CRFs will serve as the source documents for this study.

Image and video files will be gathered and stored in electronic format.

10.3 *Records retention*

Essential documents shall be archived by the Sponsor-Investigator safely and securely in such a way that they are readily available upon authorities' request for at least 2 years following completion of the study.

11 Study monitoring, auditing, and inspecting

The Sponsor-Investigator will verify that subject rights and well-being are protected. The Sponsor-Investigator (Enspectra Health) designates a hired clinical consultant to perform clinical monitoring,

including review of the CRF, before initiation and after completion of the study. The Sponsor-Investigator will allow direct access to all relevant subject files for the purpose of verifying entries made in the CRF and assist with the monitor's activities as required.

In accordance with applicable regulations, GCP, and Sponsor-Investigator procedures, the monitor will, prior to the start of the study, review with the Sponsor-Investigator representative the protocol, study requirements, and the Sponsor-Investigator's responsibility to satisfy regulatory and ethical requirements. When reviewing data collection procedures, the discussion will also include identification and documentation of source data items.

The monitor will verify that:

- The data are authentic, accurate, and complete.
- The safety and rights of the subject are being protected.
- The study is conducted in accordance with the currently approved protocol (including study treatment being used in accordance with the protocol.)
- Any other study agreements, GCP, and all applicable regulatory requirements are met.

Audits and inspections by regulatory health authority representatives and IRB are possible. The Sponsor-Investigator agrees to allow the auditor or inspector direct access to all relevant documents and allocate time to the auditor/inspector to discuss findings and any issues. Audits and inspections may occur at any time during or after completion of the study.

12 Premature termination of the study

The Sponsor has the right to close this study at any time, which may be due but not limited to the following reasons:

- If risk-benefit ratio becomes unacceptable owing to, for example
 - Safety findings from this study (e.g., SAEs).
 - Results of any interim analysis.
 - Results of parallel clinical studies.
 - Results of parallel animal studies
- If the study conduct (e.g., recruitment rate; drop-out rate; data quality; protocol compliance) does not suggest a proper completion of the trial within a reasonable time frame.
- Sponsor decision to suspend or discontinue evaluation of *VioTM*.
- Failure of the Investigator to comply with the tenets of the Study protocol, Study Investigator Agreements and Contracts, Regulatory requirements, or any applicable laws.
- Intentional submission of false study-related data and/or information by the research facility to the Sponsor.
- Sufficient data collected with smaller sample size

The Investigator will discuss with subjects any standard of care for future medical follow-up that may be required.

The Investigator has the right to close his/her center at any time.

For any of the above closures, the following applies:

- Closures should occur only after consultation between involved parties. Final decision on the closure must be in writing.
- All affected institutions (e.g., IRB(s), competent authority(ies), study center, head of study center) must be informed as applicable according to local law.
- All study materials (except documentation that has to remain stored at site) must be returned to the Sponsor. The Investigator will retain all other documents until notification given by the Sponsor for destruction.
- In case of a partial study closure, ongoing subjects, including those in post study follow-up, must be taken care of in an ethical manner.

Details for individual subject's withdrawal can be found in Section 5.4.

13 Ethical considerations

The procedures set out in this protocol, pertaining to the conduct, evaluation, and documentation of this study, are designed to ensure that the Sponsor-Investigator abide by GCP guidelines and guiding principles detailed in the Declaration of Helsinki. The study will also be carried out in keeping with applicable local law(s) and regulation(s), including ISO 14155.

Documented IRB approval will be obtained before the start of the study, according to GCP, local laws, regulations and organizations. When necessary, an extension, amendment, or renewal of the IRB approval must be obtained. The IRB must supply to the Sponsor-Investigator, upon request, a list of the IRB members involved in the vote and a statement to confirm that the IRB is organized and operates according to GCP and applicable laws and regulations.

Strict adherence to all specifications laid down in this protocol is required for all aspects of study conduct; the Sponsor-Investigator may not modify or alter the procedures described in this protocol without proper IRB approval.

The Sponsor-Investigator, however, may implement a deviation from, or a change of, the protocol to eliminate an immediate hazard(s) to the trial subjects without prior IRB approval. As soon as possible, the implemented deviation or change, the reasons for it, and if appropriate the proposed protocol amendment should be submitted to the IRB. Any deviations from the protocol must be explained and documented by the Sponsor-Investigator.

14 Publication Policy

The Sponsor-Investigator will evaluate the results of the trial and determine whether publication is appropriate, based on the investigational nature of the device and the early stage of research.

15 References

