4.1 Overview

This is a single-center, open-label, one-arm observational clinical study. Up to 120 subjects will be enrolled in the study. Each subject will participate in one session for a maximum of 3 hours, but typically

lasting an hour, including the preparation and consent process. Subjects will be monitored for AEs during and immediately following the procedure. Subjects will be requested to self-report any AEs for up to seven days following the procedure. The overall study duration is expected to be approximately 5 years

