4.2 Justification for clinical study design

Initial human testing (described in Section 1.3) demonstrates decades of scientific research confirming successful nonlinear imaging of skin *in vivo*. The study described herein will provide observational evidence for the effectiveness of the *VioTM*, a miniaturized nonlinear microscope, to display features of skin structure as well.

In this study, we plan to gather feasibility data for future studies. This feasibility data will likely inform future clinical investigations of skin disease diagnosis and may assist with sample size calculations.

5 Subject selection and withdrawal

The target patient population is composed of male and female adults and children that meet eligibility criteria described in Sections 5.1.1 through 5.1.5.

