7.3 Completion

The subject may choose to end his/her participation at any time by notifying the Investigator(s) or designee, who will immediately stop image collection. In order to minimize bias in the collection of study data, information already collected may be included in data analysis.

The successful completion of the procedures, or subject withdrawal or termination of procedures, will be documented at the end of the subject's participation. Subject participation may occur over multiple visits, as subjects are allowed to participate more than once.

Subjects may be compensated for their participation up to \$50 per session.

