8.1 Sample size determination

Although nonlinear imaging of human skin has been performed for years, little statistically meaningful data has been gathered to justify a robust sample size determination. A sample size of 120 was chosen to provide options for imaging skin of different demographics and minor technology modifications, although there are no strict requirements on enrollment of different groups for this protocol [2 (technology versions) \times 2 (sex; male, female) \times 5 (age; younger children, older children, young adults, middle aged adults, older adults) \times 5 (race/ethnicity; latino/a, black, Indian, Asian, white) = 100+(overhead)=120]. The sample size calculation for this study is justified because this study is purely observational.

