8.2 Statistical methods

The primary analysis involves the quantification of imaging performance of the *VioTM* as a function of skin type, location (e.g., forearm, ear, nose), and health of skin. Because group sizes are small, statistical comparisons are unlikely to be significant. Still, data from this study will be important for planning statistically robust future studies. As a secondary aim, image performance will also be qualitatively evaluated by physicians trained in dermatopathology interpretation. Interim analyses are not planned.

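### Does closing early for sufficient data, with no stated criterion, expose the study to result-driven stopping?

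*Combined protocol and SAP*

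**What the plan says.** Section 12 of the combined protocol and SAP gives the sponsor a right to close the study at any time and offers a list of reasons that it states is not exhaustive. Two items matter here.

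- A stand-alone item: "Sufficient data collected with smaller sample size". Nothing in the visible text says sufficient for what, or who judges it and when.
- An item nested under the lead-in "If risk-benefit ratio becomes unacceptable owing to, for example", which reads "Results of any interim analysis".

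Section 12 also requires consultation before closure and a written final decision.

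On interim looks, Section 8.2 says "Interim analyses are not planned". On size, Section 4.1 says "Up to 120 subjects will be enrolled in the study", and Section 8.1 explains that "A sample size of 120 was chosen to provide options for imaging skin of different demographics and minor technology modifications", adding that no group has a strict enrolment requirement. The study summary states that there are no established quantitative endpoints. Section 4.2 says the feasibility data "may assist with sample size calculations" for later studies.

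**The concern.** Sufficient data is an elastic phrase, and the basis on which it is judged decides its statistical effect. Stopping on head count or on coverage of skin types leaves the estimates essentially unbiased and only makes them less precise. Stopping because the images look good conditions the estimates on a favourable run and pushes them upward.

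The setting makes the second possibility more than theoretical. The study is open-label with one arm, Section 9.3 confirms there is no blinding, and under Section 2 the sponsor is also the Sponsor-Investigator and picks investigators from its own organization. Those who decide on closure may therefore have seen the images. If optimistic figures were then used to size a later study, that study could be too small. Naming interim results as a ground for closure, when Section 8.2 plans no interim analysis, seems to add an unplanned look through which this could happen.

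**Working it through.** **1. The plan's own figure.** Section 8.1 multiplies 2 technology versions × 2 sexes × 5 age groups × 5 race/ethnicity groups = 100 cells, then adds overhead to reach 120. The overhead is not stated as a number; by subtraction it is 120 − 100 = 20. The figure reproduces. It is a coverage count, with no effect size, alpha, power or precision behind it.

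**2. Loss of precision at a smaller N.** Assume one value per subject and independent subjects. The interval width relative to 120 is √(120/n).

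| n | √(120/n) | Wider by | Worst-case 95% half-width for a proportion, 1.96·√(0.25/n) |
|---|---|---|---|
| 120 | 1.000 | – | 8.9 points |
| 80 | 1.225 | 22% | 11.0 points |
| 60 | 1.414 | 41% | 12.7 points |
| 40 | 1.732 | 73% | 15.5 points |

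The values 80, 60 and 40 are illustrative; the protocol names none of them. The same ratio applies to any study that enrols fewer than its maximum. An interval calculated at the achieved n carries its own width, so a later planner sees the loss. The pooled per-subject mean is also not what Section 8.2 describes: its primary analysis is by skin type, location and skin health, and under Section 7.3 "subjects are allowed to participate more than once".

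**3. Loss of coverage.** If each subject is imaged with one technology version, the minimum number of empty cells is 100 − n: 20, 40 and 60 at n = 80, 60 and 40. Section 6.1.1 sets no enrolment target for children and says the study can be completed without them. Children make up 2 of the 5 age groups, so 2 × 2 × 2 × 5 = 40 cells may be empty at the full 120. The minimum at n = 80 (20) is below that, and at n = 60 (40) it equals it. At n = 40 it is higher (60), but Section 8.1 does not require any cell to be filled.

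If each subject is imaged with both versions, the grid is 2 × 5 × 5 = 50 demographic cells. The minimum empty is max(0, 50 − n): 0, 0 and 10. The child cells in that grid number 2 × 2 × 5 = 20, so even the 10 at n = 40 is within what is already accepted.

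**4. The two statements on interim analysis.** Section 8.2 reports that none is planned; it does not forbid one. Section 12 refers to any interim analysis, which is conditional, and offers it only as an example of how the risk-benefit ratio might become unacceptable. Both statements can hold together. If no interim analysis takes place, the item has nothing to act on. If one does, the item concerns an unfavourable balance of risk and benefit, the opposite of stopping on good images.

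**5. Would rewording exclude result-driven closure?** No. The list is expressly not exhaustive, and it also contains a plain sponsor decision to suspend or discontinue evaluation of the device. Tightening one item leaves those routes open.

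**The case for a change.** The strongest opposing case is that the basis for closure matters and the protocol could state it at almost no cost. The written decision that Section 12 requires need not record why the data were judged sufficient, and nothing obliges the sponsor to report that reason with the results. Section 8.2 says the data will matter for planning later studies, and Section 7.3 already keeps data from subjects who stop early in order to limit bias.

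Much of this is true. No visible text defines sufficient, and closure driven by favourable images would bias the estimates. A simulation shows the order of size, on inputs that are all assumed and not in the documents: a binary outcome with a true rate of 0.6 to 0.8, looks every 20 subjects up to 120, and a stop when the observed rate is at least 5 or 10 points above the truth. The study then closes early in about 23% to 55% of runs, and the mean estimate is about 2 to 4 points too high. That is what one invented rule would do. The protocol contains no such rule, outcome or schedule of looks, so the result cannot be attributed to this plan.

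What stands is a reporting preference: say why the study closed and give the final N beside the ceiling of 120. The protocol does not prevent this, and a competent report of a study that enrolled fewer than its maximum would include both.

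**Conclusion.** The concern does not call for a change. Section 12 leaves sufficient undefined, but this is missing detail in a feasibility study. No rule in the plan would give a wrong result if followed. Count or coverage is the natural reading, because Section 8.1 derives 120 from a coverage grid and Section 4.1 makes it a maximum. The interim-analysis item is compatible with Section 8.2, and deleting it would alter no result.

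The calculable effects are a 22% to 73% wider interval at 80 to 40 subjects, assuming one independent value per subject, and empty cells that at 80 or 60 subjects do not exceed the 40 the protocol tolerates at full enrolment. Neither breaches a target, because none is set. No optimism bias can be quantified from the documents, since they set no quantitative endpoint.

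This rests on the visible text. Part of Section 3 is blacked out, and a criterion could stand there.
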